Setting: The outpatient treatment center at the UF Health Cancer Center-Orlando will be the primary site for enrollment due to its long-standing relationship with these researchers. In 2013, UF Health Cancer Center-Orlando saw approximately 4,694 patients. Of these 2,573 patients were age 65 or older, and 565 of these patients received outpatient chemotherapy. These numbers indicate an ample sampling pool of older adults.

Sample size: The target sample is older adults receiving emetogenic chemotherapy for the first time. Sixty-six participants will be enrolled if they meet the following **inclusion criteria**: age 65 and older, newly diagnosed with any cancer, treatment with any chemotherapeutic agent with a moderate to severe emetic potential (on a 3- or 4- week cycle), proficient in English, and have a telephone. **Exclusion criteria** include: previous diagnosis and treatment for cancer, advanced or end stage disease with a palliative intent, visually or hearing impaired. Dementia or cognitive impairment is not a concern with the population since they have already been cognitively screened in order to consent to treatment at this cancer center. There will be no exclusion based on gender or racial/ethnic status. Retention of all participants will be enhanced by the following strategies 1) weekly telephone follow-up phone calls by the RA; 2) a \$50 incentive/gift card at the end of the study period; and 3) attention control group offered eSSET-CINV at the end of the study. We will oversample by 20% in order to account for attrition.

Phase II Procedures:

Recruitment and randomization: Successful recruitment and retention strategies previously established by the team will be used during this phase.^{7, 15, 16, 18, 90} Convenience sampling, followed by randomization will be used. All new patients will be screened for eligibility by the Research Nurse (RN-PG) using the Sunrise XA -

electronic medical record system used by Orlando Health. Eligible patients will be approached by the RN at their first chemotherapy appointment and asked to participate. This timing is not expected to add to or create patient anxiety. Patients usually wait 30 to 60 minutes for lab results and chemotherapy to be delivered. Participating

Table 1: Intervention schema

	Pre-treatment		First Treatment Visit			Post - treatment

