Participant characteristics: Demographic and experiential characteristics that may influence CINV and ability to self-manage this symptom will be measured at T1 (baseline). Demographics include: age, gender, comorbidity information, education level, and income level. Experiential characteristics include: cancer diagnosis and stage, chemotherapy regimen with antiemetics, discharge antiemetic prescriptions, use of the Internet to research symptom management information, and caregiver presence (yes/no) and involvement at home. All cancer information will be collected from the patient's electronic medical record by the RN. Delays in chemotherapy treatment and rationale for delay will also be recorded at each time point by the RN.

Dependent Variables

An overview of study variables, measures and data collection timeline are presented in Table 3. Data will be collected for 4 treatment cycles (3 or 4 months depending on cycle length). Questionnaires will use a paper/pencil format with enlarged font and be entered into Excel™ software.

1) Symptom severity: The *Symptom Representation Questionnaire (SRQ)*⁹¹, a 24-item self-report measure will be used to identify presence and severity of common treatment-related symptoms (0-10 Likert scale), including nausea and vomiting (N/V). This measure asks respondents to think about their symptoms over the past week.

Table 2: eSSET-CINV Intervention process

1	Game introduction and orientation
2	Choose avatar
3	Avatar discharged home after treatment
4	Avatar begins to experience nausea
5	Player makes self-management decisions
6	Avatar responds based on player decisions
7	Avatar experience continues with periodic nausea as player continues to make self-management decisions
8	Game ends when avatar achieves goal of mild or no nausea or has an unplanned ED or hospital admission
9	Discussion of decision choices with Research Nurse

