2) Cognitive representation: The *Symptom Representation Questionnaire (SRQ)*⁹¹ has an additional 15 questions to assess cognitive representation (identity, cause, timeline, consequences, and cure/control) or beliefs about specific symptoms (0-4 agreement scale). This measure includes subscales for symptom cause (2 questions), timeline (3 questions), cure/control (3 questions), and consequence (6 questions). Only the cognitive representation of nausea will be evaluated. This tool is reliable with alpha co-efficients from 0.63 to 0.88 for the subscales.⁹¹ The cognitive representation questions will be modified at baseline to assess participants' beliefs about potential CINV consequences and their ability to be controlled/cured. Subsequent data collection time points will focus on current cognitive representations.

3) Self-management behaviors: An investigator-developed *Symptom Management Checklist [SMC]* will measure CINV: 1) self-management behaviors and 2) prevention behaviors. Participants will complete this daily at home between chemotherapy cycles. When experiencing CINV, the participant will use the SMC to record: 1) CINV severity (0-10 Likert scale) prior to self-management, 2) the *type* of self-management strategies used and, 3) the strategies *perceived helpfulness* in reducing nausea (0-10 Likert scale). Preventative self-management activities for CINV will also be recorded. All self-management strategies are coded (e.g., “MED”= taking antiemetic, “DIS”- using distraction), and the participants will fill in the strategy code they are using on the form. To lessen the risk of the SMC becoming an intervention for the Control Group, all participants will be asked to record self-management behaviors of other common treatment-related symptoms (i.e. fatigue, mouth/throat sores). The SMC will be collected by the research nurse at chemotherapy cycles 2, 3 and 4.

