Preliminary data analysis: Descriptive statistics will be provided to characterize the study participants for all demographic and experiential variables at baseline and at each treatment cycle time point. Summary tables will be provided to present participant characteristics (e.g., gender, age group, race), major study variables, game appeal, and willingness to recommend game to others. Internal consistency of study measures will be checked and evaluated to ensure data quality. Effort will be taken as much as possible to avoid missing data. If there are significant missing data that may impact analysis results, the multiple imputation method may be used for the analysis of primary endpoint. All statistical analyses will be performed using Statistical Application Packages (SAS®), version 9.4.

Principle data analysis: The primary endpoints for the study are N/V severity score and the number of self-management behaviors. The secondary endpoints are ED/hospital admission and QOL. Summary statistics for the primary and secondary endpoints will be provided. The t-test will be used if the normality of the endpoint can be confirmed. Otherwise, the Wilcoxon Rank-Sum test will be used to assess the difference between the two groups at each treatment cycle time point.

AIM 1: Estimate effect size of the eSSET-CINV in changing patient outcomes: cognitive representation, self-management behaviors, CINV severity, QOL, and resource use. The effect size of N/V severity score will be estimated using the Cohen’s d, which is defined as the difference between two means divided by a standard deviation for the data.

AIM 2: Examine differences in cognitive representation, self-management behaviors, CINV severity, QOL, and resource use, between, and within, the intervention and attention control groups. For the primary endpoints, the data will be collected over 4 treatment cycles, and the method of analysis of longitudinal data will be used to compare the difference between intervention and control groups over time. The generalized estimating equation (GEE) approach may be used to enhance the robustness of the estimation of model parameters when the ideal working correlation structure is difficult to pre-specify. In the longitudinal model treatment cycle time, interaction of time and treatment, or both, whenever feasible, may be added into the model to assess the time effect on treatment difference.

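### The primary count of self-management behaviours has no common diary window and no adjustment for diary days completed, so unequal diary completion between arms could look like a treatment effect

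*Combined protocol and SAP*

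**What the plan says.** Under Principle data analysis (Data Analysis, Phase II): "The primary endpoints for the study are N/V severity score and the number of self-management behaviors". No unit of time or denominator is attached to the second of these.

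Item 3 of Dependent Variables gives the source, the Symptom Management Checklist (SMC). "Participants will complete this daily at home between chemotherapy cycles", and "The SMC will be collected by the research nurse at chemotherapy cycles 2, 3 and 4". Entries about managing symptoms depend on symptoms: "When experiencing CINV, the participant will use the SMC to record" severity, strategy type and helpfulness. Preventive activities are recorded as well.

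The interval varies. The inclusion criteria admit regimens "on a 3- or 4- week cycle", and under Co-variates, "Delays in chemotherapy treatment and rationale for delay will also be recorded at each time point by the RN". The delays are not linked to the behaviour count.

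Arms are compared at each cycle by t-test or Wilcoxon test, and over time by repeated-measures ANOVA or an optional GEE. No offset, exposure term, minimum number of diary days or blank-day rule is given. AIM 2 says that a time window defining the treatment cycles will be settled later. It gives no value and does not mention diary days. Multiple imputation is optional. Allocation is by choosing an envelope, with no stratification described.

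**The concern.** A count taken from a diary is the product of how often a patient acts and how many days the patient records. Only the first is of interest. Here the second varies for three reasons: cycle length, treatment delay and diary completion.

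Cycle length is fixed before randomisation, so it can add noise but not systematic bias. Delay and completion arise afterwards and may differ by arm. Only the intervention arm plays the game and discusses self-management choices with the research nurse, and that could make those patients more diligent recorders. A higher count would then reflect better record-keeping and be read as better self-management. The reverse difference in completion would hide a real benefit. Estimating the effect size is a stated Phase II aim, so a distorted ratio matters as much as a distorted p-value.

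**Working it through.** The plan gives no sample size, variance or target difference for this endpoint, so there is no figure to reproduce. From the documents: 33 per group, 1:1 allocation, intervals of 21 or 28 days, daily recording. Everything marked *assumed* is not in the documents.

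**1. Interval length within a patient.** Expected count = daily rate × days recorded.
- Constant daily rate: 28/21 = 1.33. A one-week delay of a 3-week cycle gives the same figure, and a two-week delay gives 35/21 = 1.67.
- Behaviours clustered early (*assumed*: 80% of a 21-day count falls in week 1): the other 20% over two weeks is 10% a week, so a fourth week gives 1.10. The 33% is therefore an upper bound for 28 v 21 days.

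**2. Interval length between arms.** With half the patients on 4-week cycles (*assumed*), the difference in that share between arms has SD √(2 × 0.25/33) = 0.123, with a 95% limit of 1.96 × 0.123 = 0.24. Shares of 62% and 38% give (21 + 7 × 0.62)/(21 + 7 × 0.38) = 25.34/23.66 = 1.07. Even an extreme chance imbalance moves the ratio by about 7%.

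**3. Delay.** One-week delays in 30% of controls and 10% of game patients (*assumed*): mean intervals are 24.5 + 0.3 × 7 = 26.6 and 24.5 + 0.1 × 7 = 25.2 days, and 25.2/26.6 = 0.95. Simulations gave 0.95 to 0.96, with false-positive rates of 5.1% to 5.7%. With early clustering the ratio is 0.98 to 0.99.

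**4. Diary completion.** If blank days resemble completed days, the spurious ratio is the ratio of completion: 0.80/0.70 = 1.14, 0.90/0.75 = 1.20, 0.90/0.60 = 1.50. The table comes from 20,000 simulated trials: 33 per arm, one interval, half on 21 and half on 28 days, one behaviour per day, between-patient CV 0.5, Poisson counts, two-sided t-test at 5% (apart from 33 per arm and the two cycle lengths, all *assumed*).

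| Completion, game v control | True rate ratio | Raw count: ratio; significant | Per completed day: ratio; significant |
|---|---|---|---|
| 80% v 80% | 1.0 | 1.00; 4.9% | 1.00; 4.9% |
| 90% v 75% | 1.0 | 1.20; 22.7% | 1.00; 5.0% |
| 90% v 60% | 1.0 | 1.50; 72.2% | 1.00; 4.7% |
| 80% v 80% | 1.4 | 1.40; 59.3% | 1.40; 69.6% |

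Repeat runs at 90% v 75% gave 1.21 and 21% to 22%.

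**5. Does the alternative cost power?** *Assumed*: 0.6 behaviours per day, 15% delayed by one week, rate ratio 1.4. With CV 0.4 and completion of 50% to 100%, power is 66% for the raw count and 75% per completed day in a fixed window. With full diaries and early clustering it is 79% for both. The alternative rarely loses and usually gains.

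**6. Limit of step 4.** If every blank day were truly free of behaviours, the raw count would be correct and the per-completed-day rate would show 0.75/0.90 = 0.83. Blank days must therefore be distinguishable from days with no strategy used.

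**The case against.** The strongest reply is that the plan never says it will use a raw total. The checklist records strategies by code, and the background section discusses numbers and types of strategies used. A count of distinct types per cycle is a fair reading, and it would not rise in proportion to days. This stands. A reader might infer that the endpoint is certainly a total of occurrences; the documents leave it undefined. Distinct types would still tend to rise with days recorded, though less steeply.

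A reader might also infer that blank days will be scored as zero. The documents contain no such rule and do not reproduce the form, so it may already have an entry for none. What can be said is that no rule is given. Multiple imputation needs missing days to be identified first.

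It is tempting to treat varying cycle length, or delays reduced by the game, as a serious bias. Steps 2 and 3 do not support that. With full diaries, interval length and delay alone cost little power: 77% raw v 82% per day at CV 0.4, and 52% v 55% at CV 0.6.

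The plan also has safeguards. Both arms receive weekly calls reminding them to record, which makes differential completion less likely but does not rule it out. The promised window could equalise interval length once specified, but would not address completion. Finally, this is a trial to establish effect size with no power claimed for this endpoint, so the power comparisons carry limited weight. The spurious ratio is an error in the effect estimate itself, so that argument does not remove it.

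**Conclusion.** The point holds in a limited form. A primary endpoint is worded as a bare number, drawn from a daily diary over intervals of unequal length, and compared with no common window or adjustment for days completed. What is counted and how blank days are handled are not stated.

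Interval length is mainly noise and delay bias is small. The material exposure is differential diary completion: with no true effect, 90% v 75% gives a ratio of about 1.2 and 21% to 23% false positives, against 1.0 and 5% per completed day. This assumes that the endpoint counts occurrences and that blank days resemble completed ones. The daily rate, CV, cycle mix and completion levels are also assumptions. Nothing in the documents shows that completion will differ by arm; the finding is that the plan could neither detect nor correct such a difference. This is a worthwhile, inexpensive improvement and not a fatal flaw.

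**What to change.** In the analysis section and on the checklist:

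- State what is counted: recorded occurrences or distinct strategy types, and responses to CINV, preventive actions or both. If types are chosen, count them within each day, because a cycle total of types is not proportional to days.
- Restrict the primary count to a fixed window common to both cycle lengths, for example the first 21 days after each infusion.
- Analyse behaviours per completed diary day, or the count with log(completed days) as an offset in the GEE already mentioned.
- Ensure that the checklist has a daily entry for no strategy used, so that a blank day is missing and not zero.
- Report completed diary days by arm and cycle.

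The cost is SAP wording, at most one tick-box on the form, and one table. No extra patients or visits are needed. The downside is that days 22 to 28 of 4-week cycles are described but do not enter the primary count.

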of self-management strategies used and, 3) the strategies *perceived helpfulness* in reducing nausea (0-10 Likert scale). Preventative self-management activities for CINV will also be recorded. All self-management strategies are coded (e.g., “MED”= taking antiemetic, “DIS”- using distraction), and the participants will fill in the strategy code they are using on the form. To lessen the risk of the SMC becoming an intervention for the Control Group, all participants will be asked to record self-management behaviors of other common treatment-related symptoms (i.e. fatigue, mouth/throat sores). The SMC will be collected by the research nurse at chemotherapy cycles 2, 3 and 4.

4) Health-related Quality of Life- The EORTC-30⁹² will measure QOL at each treatment cycle. This frequency is consistent with others studies that have measured QOL in older adults over time.^{59, 93} This well-known scale includes 5 functional scales, 3 symptom scales, and 6 single items using a 4-point Likert scale (“not at all” to “very much”), and 2 global health/QOL items using a 7-point Likert scale (“very poor” to “excellent”). Higher scores on the functional and health/QOL scale indicate better functioning, while higher scores on the symptom-related scales and items indicate higher symptoms. Reliabilities (Cronbach's alphas) range from 0.52 (role functioning scale) to 0.89 (QOL).⁹²

5) Resource Use: Any unplanned Emergency Department or hospital admission will be recorded via participant report using a dichotomous (Y/N) variable at each follow-up phone contact and treatment visit. Follow-up questions about the reason for the admission, length of time for admission and treatment will also be asked. The report will be verified by medical record review whenever possible.

Additional Outcomes:

Game appeal: Under the guidance of the PI, student RAs will develop and pre-test a short survey to evaluate game appeal at the first follow-up phone call. Using a 4-point agreement scale, participants will be asked the extent to which they agree or disagree with statements regarding ease of game play, game likability, clarity of self-management choices, usefulness in educating about CINV consequences and ability to be controlled/cured, and realism (setting and scenario). Additional comments about the game will be recorded.

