The one-way repeated measures ANOVA will be used to assess the difference between the two groups. The mixed effect model may be used as exploratory analysis to account for unobservable variations from each individual patient. In addition, comparisons between two groups at each treatment cycle time point will be performed for all primary and secondary endpoints. For this particular comparison, the univariate normality of each endpoint will be assessed graphically at each treatment cycle time point. An appropriate time window will be determined to define the treatment cycles for the study.

AIM 3: Obtain preliminary data regarding the feasibility and acceptability of the game in older adults experiencing CINV. Feasibility- Computer science and digital media undergraduate students will work under the direction of [name] and [name] to identify patterns in game play data (e.g., self-management decisions, scenario patterns of progression), time to game completion, and number of times the game was played (intervention dose). The RN will track any instance of game play interruptions or

malfuction. This data will be summarized with descriptive statistics. **Game Appeal:** Responses to the game appeal and willingness to recommend questions will be scored and summed using descriptive statistics. Additional comments about the game will be recorded and analyzed for themes.

Sample size and statistical power:

Based on the assumption of a nausea severity mean score of 6.20, range from 2 to 9, a standard deviation of 2.44, and a clinically meaningful difference in mean nausea severity score of one between the intervention and control groups, with 90% power, the required sample size is 33 participants for each group, yielding a total sample size of 66 for the study. To reduce the patient selection bias, single-blinded randomization may be used whenever feasible. Due to lack of available data from prior research the sample size for secondary endpoints is not possible for the study at first stage. However, the power statistical analysis will be assessed when data become available from the planned study.

Potential challenges and strategies for addressing:

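### Two primary endpoints, each tested at three cycles and again longitudinally, with no deciding test and no rule for sharing the error rate

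*Combined protocol and SAP*

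**What the plan says.** Principle data analysis (Data Analysis, Phase II) sets two primaries: "The primary endpoints for the study are N/V severity score and the number of self-management behaviors". The first between-group method it names is a t-test where normality is confirmed; failing that, "the Wilcoxon Rank-Sum test will be used to assess the difference between the two groups at each treatment cycle time point".

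Under Aim 2 the primary endpoints also get a longitudinal comparison of the groups over time, for which GEE may be used and to which time and time-by-treatment terms may be added. A repeated measures ANOVA of the group difference follows, then a mixed model labelled exploratory. The per-cycle tests then return: "In addition, comparisons between two groups at each treatment cycle time point will be performed for all primary and secondary endpoints".

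Table 3 schedules symptom severity at T1 to T4 and self-management behaviors at T2 to T4. On the latter, the Dependent Variables section agrees: "The SMC will be collected by the research nurse at chemotherapy cycles 2, 3 and 4". Both primaries therefore have three post-baseline time points.

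Sample size and statistical power uses nausea severity alone, at 90% power, and concludes that "the required sample size is 33 participants for each group, yielding a total sample size of 66 for the study". It explains why secondary endpoints were not sized and does not mention the number of self-management behaviors. No alpha, sidedness, hierarchy, either/both rule or multiplicity adjustment appears in the text supplied.

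**The concern.** With two primary endpoints and several planned tests of each, the analyst needs to know in advance which result answers the question. Here three kinds of between-group test (per-cycle, longitudinal, ANOVA) apply to the same data, and none is called decisive. A report could follow the plan faithfully and still present whichever cycle, method or endpoint gave the smallest p-value as the primary finding.

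The error rate attached to a positive primary result is then unknown, and it exceeds the nominal level under any reading in which one success is enough. The number of self-management behaviors is also exposed on the other side: with no sample size behind it, a null result on that endpoint would be hard to interpret.

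**Working it through.** **Inputs from the documents.** Two primary endpoints; three post-baseline time points each (Table 3); 33 per group; difference 1 point; SD 2.44; 90% power.

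**Assumptions, because the documents are silent.** Two-sided 0.05 per test; between-visit correlation 0 to 0.9; between-endpoint correlation 0 to 0.5; no true effect on either endpoint; success on either endpoint counts.

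**The plan's own figure.** The documents give no family-wise error rate to reproduce. Their one related figure, 33 per group, does not follow from its stated inputs by the usual two-sample formula: n = 2 × 2.44² × (1.960 + 1.282)² = 125.1, so 126 per group at two-sided 0.05 and 90% power. That is a separate problem. It does not enter the error rates below, but it does affect the cost of the fix.

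**Reading A: any per-cycle result counts.** This gives 2 × 3 = 6 tests. If they are independent, 1 − 0.95⁶ = 26.5%. Tests on the same patients are correlated, so six correlated normal test statistics were simulated (1,000,000 draws per cell, equal correlation between visits). Probability of at least one p < 0.05:

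| Between-visit correlation | Endpoints independent | Endpoint correlation 0.3 | Endpoint correlation 0.5 |
|---|---|---|---|
| 0 | 26.5% | 25.9% | 24.8% |
| 0.5 | 23.6% | 23.0% | 22.0% |
| 0.7 | 20.7% | 20.2% | 19.2% |
| 0.9 | 16.1% | 15.6% | 14.8% |

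Simulated t-tests at 33 per group (40,000 trials, independent endpoints) agree: 26.5%, 23.4% and 20.4% at between-visit correlations 0, 0.5 and 0.7. The range is about 15-26%.

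**Reading B: one longitudinal test per endpoint decides, and either may succeed.** 1 − 0.95² = 9.75%, about 10%, with independent endpoints.

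**Sensitivity.** At 0.025 per test, six independent tests give 1 − 0.975⁶ = 14.1%; the same figure applies if only errors in the game's favour are counted. Counting the longitudinal and ANOVA tests as further chances would raise Reading A. Requiring success on both endpoints, with one test each, would hold the rate at 5% or below, but the plan does not say this.

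**Cost of splitting alpha.** Single-visit t-test, 33 per group: noncentrality = (1/2.44) × √(33/2) = 1.665 on 64 degrees of freedom. Power is about 37% at 0.05 (critical value 1.998) and about 27% at 0.025 (critical value 2.295).

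**The case against.** The strongest reply is that Phase II is described as a trial to establish effect size, that Aim 1 is estimation, and that the sample size section speaks of a first stage; strict error control matters less in such a study. This stands in part, and it argues for estimates over tests. It does not remove the problem: Aim 2 compares the groups by tests, and the sample size is justified by 90% power, which presupposes a test at some alpha.

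A second reply is that the longitudinal comparison is the real primary analysis. Aim 2 assigns it to the primary endpoints and introduces the per-cycle comparisons as additional. That reading is open, and it is why the lower figure of about 10% belongs in the conclusion. It is not settled, because the Principle data analysis paragraph itself names per-cycle tests.

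A reader might infer more than the documents support in three ways:

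- That the error rate simply is 20% or higher. That needs any per-cycle result to count, an alpha the plan never states, and only moderate correlation between visits.
- That a false positive would trigger dissemination. The plan speaks of dissemination once effectiveness is shown, but attaches no action to a p-value, and Table 4 schedules dissemination and final grant reports whatever the result.
- That every EORTC score will be tested at every visit. The instrument has "5 functional scales, 3 symptom scales, and 6 single items" plus global items, but QOL is a secondary endpoint and the plan does not say which scores will be tested.

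**Conclusion.** The concern holds in this form: two primary endpoints, several planned between-group tests of each, and no statement of which test decides or how the endpoints share the error rate. At an assumed two-sided 0.05 per test, the chance of at least one false positive primary result is about 15-26% if any per-cycle result counts. It is about 10% if one longitudinal test per endpoint decides and either may succeed. The width of the first range comes from the unstated correlations; the gap between the two figures comes from the plan not choosing. Even the more favourable of these readings roughly doubles a nominal 5%. Separately, only one of the two primaries has a sample size calculation. The defect is one of specification and can be repaired before analysis.

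**What to change.** For each primary endpoint, name one deciding contrast and state alpha and sidedness. A natural choice is the between-group difference averaged over T2-T4, from the longitudinal model already planned. Then choose one of two rules:

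- **Holm across the two primaries.** The smaller p-value is tested at 0.025 and, if that succeeds, the larger at 0.05. For two independent endpoints, 1 − 0.975² = 4.9% false positives overall.
- **A fixed ranking, if the investigators prefer it.** Nausea severity, the only endpoint sized, is tested first at 0.05; self-management behaviors are tested only if it succeeds. The ranking is a judgement, since behavior change is the intervention's direct target.

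Report per-cycle differences as estimates with 95% confidence intervals, not as further tests of the primary endpoints, and label the repeated measures ANOVA as supportive or remove it. State that the number of self-management behaviors has no sample size calculation, or add one.

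The cost is SAP wording, with no new data or participants. Holm also costs power at its first step: about 37% to 27% for a single-visit t-test at the plan's own difference, SD and group size. The averaged contrast will have different power, depending on the between-visit correlation. Ranking costs nothing for the first-ranked endpoint.

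### Yes/no ED/hospital admission endpoint is tested only cycle by cycle under a t-test/Wilcoxon rule, with no overall comparison and no planned risk difference with confidence interval

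*Combined protocol and SAP*

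**What the plan says.** **Endpoint.** The Principle data analysis paragraph states: "The secondary endpoints are ED/hospital admission and QOL". Under Dependent Variables, item 5 (Resource Use), admission is recorded "using a dichotomous (Y/N) variable at each follow-up phone contact and treatment visit". Table 3 marks resource use at T2, T3 and T4 and not at baseline, which gives three windows.

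**Test rule.** The same paragraph makes its first choice of test conditional: "The t-test will be used if the normality of the endpoint can be confirmed". If that condition fails, the plan falls back on a rank test, cycle by cycle: "Otherwise, the Wilcoxon Rank-Sum test will be used to assess the difference between the two groups at each treatment cycle time point". The Aim 2 text sets the scope: "comparisons between two groups at each treatment cycle time point will be performed for all primary and secondary endpoints". It adds how the condition is to be judged there: "the univariate normality of each endpoint will be assessed graphically at each treatment cycle time point".

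**Other models.** The longitudinal analysis, with GEE as an option, opens with "For the primary endpoints, the data will be collected over 4 treatment cycles". The repeated measures ANOVA and the exploratory mixed model that follow name no endpoint and are not described for binary data.

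**Effect size.** Phase II Aim 1 lists resource use among the outcomes whose effect size will be estimated. The only measure defined is for another outcome: "The effect size of N/V severity score will be estimated using the Cohen’s d".

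The analysis section names no method for binary data, no any-admission summary, no risk difference, risk ratio or odds ratio with an interval, and no multiplicity adjustment.

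**The concern.** The rule was written for continuous scores. Applied literally, it asks the analyst to judge by eye whether a 0/1 variable is normal, and then gives three separate p-values with no statement of which one answers the question.

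Phase II is described as a trial to establish effect size, and fewer unplanned admissions is part of both the study hypothesis and the significance argument. The sample size section says that secondary endpoints could not be sized for lack of data and that power will be assessed once this trial has reported. An admission risk in each arm, and the difference with its uncertainty, is therefore what a later trial would need. The plan does not commit to producing it.

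**Working it through.** **Inputs.** From the documents: 33 per arm (sample size section), 1:1 allocation, three windows (Table 3), yes/no endpoint. The 33 was set for nausea severity (difference 1, SD 2.44, 90% power). The usual two-sample formula does not return it: 2 × (1.96 + 1.282)² × 2.44² / 1² = 125.1, or 126 per arm. That is a separate matter, and 33 is used here only as the number of patients. No power figure is stated for admission, so there is none to reproduce. Assumed: two-sided 5% level (not stated in the plan); per-cycle risks of 10% vs 3%, 15% vs 5% and 20% vs 10%; within-patient correlation from 0 to 0.8.

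**Step 1: does the choice of test matter?** Let a and b be the events per arm, n = 33, N = 66 and k = a + b. On 0/1 data the rank-sum statistic reduces to U − n²/2 = n(a − b)/2, with tie-corrected variance n²k(N − k)/[4(N − 1)]. Hence

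z² = (a − b)²(N − 1)/[k(N − k)], while Pearson χ² = (a − b)²N/[k(N − k)].

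The ratio is 65/66. With 7 vs 3 events, χ² = 16 × 66/(10 × 56) = 1.89 and z² = 16 × 65/560 = 1.86. By exact enumeration at 20% vs 10%, power is 21.0% (t-test), 20.9% (Wilcoxon), 21.0% (chi-square) and 11.5% (Fisher).

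**Step 2: events per cycle.** Expected events per arm are 33 × risk: 3.3 vs 1.0, 5.0 vs 1.7, and 6.6 vs 3.3.

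**Step 3: risk of any admission over three windows.** If cycles are independent, the risk is 1 − (1 − p)³. With correlation ρ (beta-binomial), set s = 1/ρ − 1 and β = (1 − p)s; the risk is 1 − ∏(β + j)/(s + j) for j = 0, 1, 2. For p = 0.10 and ρ = 0.4: s = 1.5, β = 1.35, and 1 − 0.900 × 0.940 × 0.957 = 0.190.

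**Step 4: power, by exact enumeration of all 2×2 tables at 33 per arm (Wilcoxon with tie and continuity correction).**

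| Per-cycle risk | One cycle, Wilcoxon | Correlation | Any-admission risk | Pooled Wilcoxon | Pooled chi-square | Pooled Fisher |
|---|---|---|---|---|---|---|
| 10% vs 3% | 19.8% | 0 | 27.1% vs 8.7% | 50.7% | 51.3% | 38.0% |
| | | 0.4 | 19.0% vs 6.0% | 38.5% | 38.6% | 21.2% |
| | | 0.8 | 12.8% vs 3.9% | 26.7% | 26.8% | 8.8% |
| 15% vs 5% | 29.1% | 0 | 38.6% vs 14.3% | 61.1% | 63.7% | 51.0% |
| | | 0.4 | 27.6% vs 9.8% | 46.3% | 47.2% | 34.5% |
| | | 0.8 | 18.9% vs 6.5% | 34.9% | 35.0% | 19.0% |
| 20% vs 10% | 20.9% | 0 | 48.8% vs 27.1% | 45.4% | 47.2% | 36.8% |
| | | 0.4 | 35.6% vs 19.0% | 31.5% | 33.9% | 23.1% |
| | | 0.8 | 24.9% vs 12.8% | 23.6% | 24.5% | 15.5% |

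**Step 5: multiplicity.** Three independent tests at 5% give 1 − 0.95³ = 14.3%. This is an upper figure: the exact size of one per-cycle Wilcoxon is 3.3% at a 5% risk and 5.6% at a 10% risk. The chance that at least one of three independent tests rejects is 1 − (1 − power)³, or 48%, 64% and 51% in the three scenarios.

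**The case against.** **A reader might infer that the plan halves the power for this endpoint.** The documents do not support that. They give no admission rates, and a factor of about one half needs both assumed rates and independent cycles. The protocol's Background says that patients with nausea in cycle 1 are more likely to report it later, so positive correlation is plausible for the symptom behind these admissions. At correlation 0.8 the pooled gain is only about 3 to 7 percentage points. One per-cycle test is also not the whole plan: the chance that at least one of three rejects (48/64/51% if independent) is close to pooled power (51/61/45%), at the price of the inflated error rate. The sound objection is therefore unadjusted multiplicity and no single answer, with lost power as a further, assumption-dependent cost.

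**A reader might infer that the t-test or Wilcoxon is what does the damage.** Step 1 shows that it is not.

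**A reader might infer that the trial would yield no risk difference.** This is too strong. Summary statistics are promised for secondary endpoints, and a crude difference could be calculated from counts. What is missing is a named measure with an interval for the whole follow-up.

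**A reader might infer that Cohen's d is to be applied to admissions.** The text assigns it only to nausea and vomiting severity. The gap for resource use is an omission.

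It can also be said that this is a secondary endpoint in a small trial that openly did not size its secondary endpoints. That limits the weight of the point. It does not remove the mismatch between endpoint and rule.

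**Conclusion.** The point holds in limited form. A yes/no endpoint is sent through a normality check it cannot pass and is then tested separately at three time points without adjustment. No overall comparison and no risk difference with interval are planned, although an effect size for resource use is promised.

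The multiplicity figure of up to about 14% assumes independent tests. The power cost of splitting rests on assumed rates, a two-sided 5% level and the correlation: from 20/29/21% per cycle to 51/61/45% pooled if independent, 39/46/32% at correlation 0.4 and 27/35/24% at 0.8. Pooling with the same test was better in every scenario here, but power stays modest. Precision is limited too: at 48.8% vs 27.1%, the standard error of the difference is √(0.488 × 0.512/33 + 0.271 × 0.729/33) = 0.116, so a simple 95% interval is about ±23 points. The emphasis belongs on estimation. The change should be made, but the trial does not stand or fall by it.

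**What to change.** For ED/hospital admission, replace the per-cycle t-test/Wilcoxon rule in the Principle data analysis and Aim 2 text with one prespecified comparison: any unplanned ED visit or hospital admission from T1 through T4, yes or no. Report the risk in each arm and the risk difference with a 95% CI (Newcombe or Miettinen-Nurminen), and name that difference as the Aim 1 effect size for resource use. Give per-cycle counts descriptively and exempt this endpoint from the normality check.

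If a p-value is wanted, take it from a score or chi-square test consistent with the interval. Fisher's test is not a good choice here. Its null rejection rate at a 10% risk is 1.2%, and its pooled power falls to 14/27/19% at correlation 0.6, below the 20/29/21% of the per-cycle Wilcoxon it would replace.

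Cost: wording only, since admissions are already asked about at every call and visit. Cycle-specific testing is given up. The plan must also say how patients with incomplete follow-up are counted, since attrition is expected (20% oversampling); the medical record review already foreseen could complete some of these.
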